#### 5.2.2.3.2 Reporting Events to the Institutional Review Board

Events meeting current UChicago IRB reporting criteria must be submitted by the principal investigator via the IRB's electronic submission system within the IRB's designated reporting timeframes. Details of the IRB's current reporting policy and timelines can be found on their website at: <http://bsdirb.bsd.uchicago.edu/forms-guidelines/up.html> .

The responsible UChicago research nurse and/or clinical research associate/data manager are responsible for entering the appropriate information into the IRB's electronic submission system and forwarding the submission to the principal investigator for reporting to the IRB.

Events occurring at a participating site should be reported to the local IRB of record according to their policies and procedures.

#### 5.2.2.3.3 Reporting Events to Boehringer Ingelheim Pharmaceuticals

Each site shall report all SAEs and non-serious AEs occurring at the same time and/or which are medically related to the SAE and Adverse Events of Special Interest by fax:

[contact]

using the BI SAE report form or alternatively CIOMS/MEDWATCH form with BI cover letter form to the BI Unique Entry Point in accordance with the following timelines:

within five (5) calendar days upon receipt of initial and follow-up SAEs containing at least one fatal or immediately life-threatening event;  
within ten (10) calendar days upon receipt of any other initial and follow-up SAEs.

#### 5.2.2.3.5 Reporting Events to Participating Investigators

It is the responsibility of the assigned CCTO Regulatory Manager on behalf of the IND Holder to notify all participating sites of all unexpected and serious suspected adverse reactions that occur on this clinical trial and which are reported to the FDA as an IND Safety Report (21 CFR 312.32). A copy of the completed Form 3500A (MedWatch) and/or IND Safety Report Narrative will be provided to the responsible Regulatory Manager by the IND Coordinator for distribution to all participating sites.

#### 5.2.2.4 Adverse Events of Special Interest

Although rare, drug-induced liver injury (DILI) is under constant surveillance by sponsors and regulators and is considered a protocol-specified significant adverse event. Timely detection, evaluation, and follow-up of laboratory alterations of selected liver laboratory parameters to distinguish an effect of the underlying malignancy on liver function from other causes are important for patient safety. The following are considered as Protocol-specified significant events:

Hepatic injury defined by the following alterations of liver parameters:

- For patients with normal liver function (ALT, AST and bilirubin within normal limits) at baseline, an elevation of AST and/or ALT  $>3$  fold ULN combined with an elevation of bilirubin  $>2$  fold ULN measured in the same blood draw sample. Patients showing these lab abnormalities need to be followed up according to this clinical trial protocol.
- For patients with abnormal liver function at baseline, an elevation of AST and/or ALT  $>5$  fold ULN combined with an elevation of bilirubin  $>2$  fold ULN measured in the same blood draw sample. Patients showing these lab abnormalities need to be followed up according to this clinical trial protocol.

Protocol-specified significant events are to be reported in an expedited manner similar to Serious Adverse Events, even if they do not meet any of the seriousness criteria - for details please see section 5.2.2.2.

If the investigator determines any protocol-specific significant event is related to study drug, the administration of the study drug must be managed according to section 4.1.3 of the protocol.

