**Table 4.1.3.2:1 Dose reduction/dose discontinuation scheme**

AE Type and grade	Action	Dose reduction/ discontinuation scheme
Grade 4 rash	Permanently discontinue afatinib	Permanently discontinue afatinib
Grade $\geq 3$ interstitial lung disease	Permanently discontinue afatinib	Permanently discontinue afatinib
Grade 4 hepatic impairment	Permanently discontinue afatinib	Permanently discontinue afatinib
Grade $\geq 3$ keratitis	Permanently discontinue afatinib	Permanently discontinue afatinib
Grade 2 left ventricular dysfunction (i.e., new resting ejection fraction of 40-50%; OR a 10-19% drop from baseline) 	Pause treatment with afatinib for 14 days and then repeat MUGA scan. If the ejection fraction has resolved to grade 1 or better at the time of the repeat MUGA, study drug will be resumed. If the toxicity has not resolved, afatinib should be permanently discontinued.	If patient was receiving 40 mg, resume treatment at 30 mg  . If patient was receiving 30 mg, resume treatment at 20 mg  . If patient was receiving 20 mg, discontinue afatinib.
Any symptomatic (grade $\geq 3$ ) left ventricular dysfunction 	Permanently discontinue afatinib	Permanently discontinue afatinib
CTCAE grade $\geq 2$ diarrhea persisting for 2 or more consecutive days (48 hours) despite adequate anti-diarrheal medication/hydration	Pause treatment with afatinib until toxicity has recovered to CTCAE grade $\leq 1$ or baseline  . If patient has not recovered to CTCAE grade $\leq 1$ within 14 days, study treatment should be permanently discontinued 	If patient was receiving 40 mg, resume treatment at 30 mg  . If patient was receiving 30 mg, resume treatment at 20 mg  . If patient was receiving 20 mg, discontinue afatinib.
CTCAE grade $\geq 2$ nausea and/or vomiting persisting for 3 or more consecutive days despite anti-emetic treatment/hydration		
CTCAE grade 2 or grade 3 worsening of renal function as measured by serum creatinine, newly developed proteinuria, or newly developed decrease in glomerular filtration rate of more than 50% from baseline		
CTCAE grade 4 worsening of renal function	Permanently discontinue afatinib	Permanently discontinue afatinib

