Any other drug related AE CTCAE grade $\geq 3$	Pause treatment with afatinib until toxicity has recovered to CTCAE grade $\leq 1$ or baseline  . If patient has not recovered to CTCAE grade $\leq 1$ within 14 days, study treatment should be permanently discontinued 	If patient was receiving 40 mg, resume treatment at 30 mg  . If patient was receiving 30 mg, resume treatment at 20 mg  . If patient was receiving 20 mg, discontinue afatinib.

 Baseline is defined as the CTCAE grade until start of treatment In the event that the patient is deriving obvious clinical benefit in the opinion of the investigator, but has not recovered within 14 days, the further treatment of the patient will be decided by the lead PI who may consult with the appropriate individuals at BI. Once a dose reduction is applied, the reduced dose is maintained unless further dose reduction is needed. Defined according to CTCAE version 4.0, page 109, adverse event denoted as “ejection fraction decreased”

 Defined according to CTCAE version 4.0, page 9, adverse event denoted as “left ventricular systolic dysfunction”

Dose reduction should always follow a treatment pause. In the event of a treatment pause, subsequent visits/courses should not be delayed.

In the event of a prolonged ( $\geq 7$  consecutive days) Grade 2 drug-related event not listed in Table 4.1.3.2:1, which is poorly tolerated by the patient, the treating investigator may choose to pause the medication for up to 14 days to allow the patient to recover followed by a dose reduction according to the schedule in Table 4.1.3.2:1.

In the event of any unrelated adverse events or unrelated serious adverse events, the treating investigator may choose to pause the medication for up to 7 days to allow the patient to recover, but no dose reduction should occur. If the treating investigator chooses to pause the medication for more than 7 days and believes that the patient would derive clinical benefit from continuing medication, the decision to continue medication will be made by the lead investigator who may consult with BI’s medical monitor.

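### Table 4.1.3.2:1 has no row keyed to the section 5.2.2.4 liver-injury definition, so a drug-related case from a normal baseline with both values below grade 3 carries no mandatory pause and no early retest

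*Combined protocol and SAP*

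**What the plan says.** Section 5.2.2.4 defines hepatic injury by two values in the same blood draw. With normal liver tests at baseline, the trigger is AST and/or ALT above 3x ULN with bilirubin above 2x ULN. With abnormal tests at baseline, the AST/ALT threshold is 5x ULN. The event is reported in an expedited manner, patients are to be followed up as the protocol provides, and for a drug-related event "the administration of the study drug must be managed according to section 4.1.3 of the protocol".

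Section 4.1.3 leads to Table 4.1.3.2:1. The parts that bear on this event are:

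- The row "Grade 4 hepatic impairment": permanent discontinuation.
- The row beginning "Any other drug related AE CTCAE grade", set at grade 3 or more: pause, then resume at a lower dose. If the patient has not recovered to grade 1 or less "within 14 days, study treatment should be permanently discontinued", subject to footnote 2, which lets the lead PI decide for a patient who is clearly benefiting.
- The text after the table: an optional pause for a "Grade 2 drug-related event not listed in Table 4.1.3.2:1, which is poorly tolerated by the patient", provided that it has lasted at least 7 consecutive days.

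Other organ signals are handled below grade 3. The row "CTCAE grade 2 or grade 3 worsening of renal function as measured by serum creatinine" carries a mandatory pause. For grade 2 left ventricular dysfunction the instruction is "Pause treatment with afatinib for 14 days and then repeat MUGA scan". Section 4.2.1 asks for interruption while suspected interstitial lung disease is investigated.

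**The concern.** Section 5.2.2.4 describes prompt detection, evaluation and follow-up of this event as a matter of patient safety and makes the referral to section 4.1.3 compulsory. For part of the event's range, that referral ends at a table that requires nothing. The only clause left is optional, and it turns on tolerability, which a laboratory finding without symptoms may never meet. Followed as written, the plan lets daily afatinib continue at the current dose after the investigator has judged the liver injury drug-related, with no test set before the next routine visit. The stake is the safety of a few patients. The trial's type I error and power are not affected.

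**Working it through.** No stated figure has to be reproduced. The check compares the definition with the table and then works out the time to the next required test.

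**1. Which cases escape the mandatory rows.** Let a and b be the multiples of ULN above which AST/ALT and bilirubin reach grade 3. Section 5.2.1 adopts CTCAE version 4.0, but the documents do not print its liver limits, so a and b are assumptions. For a normal baseline, a case meets the definition with both values below grade 3 when

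3 < AST/ALT ≤ a and 2 < bilirubin ≤ b (multiples of ULN).

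The band is non-empty only if a > 3 and b > 2.

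| Assumed a | Assumed b | Band, normal baseline |
|---|---|---|
| 5 | 3 | AST/ALT >3 to 5x, bilirubin >2 to 3x |
| 4 | 2.5 | AST/ALT >3 to 4x, bilirubin >2 to 2.5x |
| 3 | any | empty |
| any | 2 | empty |

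Example with a = 5 and b = 3: AST at 4x and bilirubin at 2.5x meets the definition (4 > 3 and 2.5 > 2), while neither value is grade 3 (4 ≤ 5 and 2.5 ≤ 3).

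For an abnormal baseline the condition is 5 < AST/ALT ≤ a and 2 < bilirubin ≤ b. This is empty unless a > 5, so at a = 5 every such case already reaches the mandatory pause.

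**2. Whether grading closes the band.** A site that grades the combined event as a single grade 3 AE would apply the catch-all row, and there would be no gap. The documents do not settle this. The ejection-fraction row has a footnote, "Defined according to CTCAE version 4.0, page 109, adverse event denoted as", naming its term, but the hepatic row names no CTCAE term.

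**3. Time to the next required chemistry.** The Flow Chart with 56-day cycles puts chemistry, which includes AST, ALT and total bilirubin, on these days:

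- Cycle 1: days 1, 15, 29 and 43.
- Cycle 2: days 57, 57 + 14 = 71 and 57 + 28 = 85.
- Later cycles: days 113, 141, 169 and so on.

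Spacing is 14 days up to day 85 and 28 days after it. Each visit has a window of ±4 days, so an interval can shift by 4 + 4 = 8 days:

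- Up to day 85: 14 − 8 = 6 to 14 + 8 = 22 days.
- From day 85: 28 − 8 = 20 to 28 + 8 = 36 days.

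With one dose a day, up to 22 or 36 further doses at 40, 30 or 20 mg could be taken before the next required test.

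**4. Whether another section fills the gap.** Section 5.2.2.2 requires AEs to be followed until resolved or sufficiently characterized, but gives no interval. Section 3.3.4 allows stopping for an unacceptable event, at discretion. No section requires a dosing action or an event-triggered retest for this band.

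**The case against.** The strongest reply is that the referral works where it matters most. Grade 4 hepatic impairment means stopping, and any drug-related event of grade 3 or more means a pause. A reader might infer that the table ignores liver injury altogether; these two rows show that it does not. Grade 3 is the table's default for a mandatory pause, and grade 2 rash likewise has only an optional one (section 4.2.3.3). The remaining band needs a normal baseline, two values in a limited range, attribution to the drug, and a site that does not grade the combination as 3. Section 5.2.2.4 itself calls drug-induced liver injury rare. Reporting is due the same or next business day (section 5.2.2.3.1), safety is reviewed weekly (section 8.1, Data and Safety Monitoring), and investigators may stop treatment. All of this stands and keeps the point minor. None of it requires a dosing action or sets a retest date.

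Three further inferences should be resisted:

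- That liver tests are not repeated at all. They are, on the routine schedule. The renal and catch-all rows set no retest date either.
- That after day 85 routine draws come too late to show recovery following a voluntary pause. The 14-day recover-or-stop limit belongs to the table's mandatory pauses. The optional grade 2 pause names no recovery grade and no stop for non-recovery.
- That section 5.2.3 gives general discretion for extra liver tests. Its sentence on extra blood examinations concerns neutropenia only.

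**Conclusion.** The point holds in a limited form. No row of Table 4.1.3.2:1 is keyed to the section 5.2.2.4 definition. Within the band, a drug-related case from a normal baseline has no mandatory pause and no retest before routine chemistry, which may be up to 22 days away, or 36 days from day 85. This rests on grade 3 starting above 3x ULN for AST/ALT and above 2x ULN for bilirubin, and on the site not grading the combined event as 3. Confidence is medium because the documents fix neither. Incidence is not given. The protocol already requires action below grade 3 for kidney, heart and suspected lung injury, so treating its own flagged liver event less strictly looks unintended. Severity is minor: a cheap improvement. A reader might infer that the trial leaves liver toxicity unmanaged; the grade 4 row, the catch-all row, routine chemistry and expedited reporting rule that out.

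**What to change.** Add one row to Table 4.1.3.2:1 for any event that meets the section 5.2.2.4 definition and is judged drug-related, whatever the grades of its components:

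- Pause afatinib and evaluate other causes.
- Repeat AST, ALT and bilirubin within 7 days, and again before the 14-day recovery limit if not resolved. The 7-day repeat keeps a case re-attributed to another cause within the 7-day pause that the text after the table allows for unrelated events.
- Then resume at a reduced dose or discontinue under the table's existing recovery rule, including footnote 2.
- Grade 4 remains permanent discontinuation.

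Point the follow-up sentences in section 5.2.2.4 to this row. Reporting rules need no change.

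The cost is one row and one cross-reference in an amendment, a few unscheduled blood draws, and an occasional pause or dose reduction in a rare event. A patient already at 20 mg would have to stop under the table's scheme. Under section 7.2, a stop before 6 months counts as a failure on the primary endpoint.

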### **5.2.3 Assessment of safety laboratory parameters**

Blood samples will be collected at the time points specified in the Flow Chart and analyzed in a laboratory facility at (or close to) the investigational site. Safety laboratory examinations include hematology and biochemistry. In case of neutropenia, blood will be examined as clinically indicated at the discretion of the treating investigator until recovery.

Safety laboratory assessment may be performed according to local practice but must include at least the following parameters:

Hematology	Red blood cell count (RBC), neutrophils, hemoglobin, white blood cell count (WBC) and differential, platelets.
Biochemistry	Sodium, potassium, calcium, magnesium, creatinine, aspartate aminotransferase (AST), alanine aminotransferase (ALT), alkaline phosphatase, total bilirubin, urea (BUN), PO4. Glomerular Filtration Rate (GFR) will be estimated by the modified Cockcroft Gault, MDRD, or CKD-EPI Formula utilizing serum creatinine values

### **5.2.4 Assessment of other safety parameters**

#### **5.2.4.1 Physical examination, performance score**

A physical examination will be performed at screening and at the time points specified in the Flow Chart.

A full physical exam serves as a clinical tumor assessment and should include a cardiopulmonary examination and an assessment of the mental and neurological status. Additional symptoms which have not been reported during a previous examination should be clarified. Wherever possible the same investigator should perform this examination.

Measurement of height (in cm), body weight (in kg) and body temperature and the evaluation of the ECOG performance score will be performed at the time points specified in the Flow Chart.

#### **5.2.4.2 Left ventricular function**

Left Ventricular Ejection Fraction (LVEF) as measured by Multi-Gated Acquisition Scan (MUGA) will be assessed at time points specified in the Flow Chart.

#### 5.2.4.3 Vital signs

Vital signs (blood pressure and pulse after 2 minutes supine rest) and temperature will be recorded at the screening visit and at the time points specified in the Flow Chart.

### 5.3 OTHER

#### 5.3.1 Demographics and history

Demographics (sex, birth date), information on smoking and alcohol history, and baseline conditions will be collected during the screening visit.

The date of first histological diagnosis (month and year may be sufficient) and type of tumor histology will be reported in the CRF. The number and locations of metastatic sites (liver, lung, peritoneum, brain, other) as well as the stage according to the tumor, (lymph) node, metastasis (TNM) classification will be provided as obtained at diagnosis and at the inclusion into the trial. Previous surgery and radiotherapy will be reported.

Previously administered chemo- or radiotherapy will be reported including start and end dates (month and year may be sufficient), the therapy protocol with the number of courses (chemotherapy), total radiation dose and radiation field (radiotherapy) and the best response obtained (complete response, partial response, stable disease, progressive disease, unknown).

### 5.4 APPROPRIATENESS OF MEASUREMENTS

The RECIST criteria 1.1 to be used for evaluation of tumor response are well established and scientifically accepted. The US NCI CTCAE criteria Version 4.0 are used in the assessment of adverse events in cancer patients. Lesions that have been irradiated as the most recent line of treatment are not eligible as RECIST target lesions.

## 6. INVESTIGATIONAL PLAN

### 6.1 VISIT SCHEDULE

Patients must be seen to complete the informed consent process in person and to undergo a baseline assessment according to the Flow Chart. After screening and registration, the patient will be seen on Day 1 of treatment initiation, and every 2 weeks during study treatment for the first 12 weeks. After 12 weeks, patients remaining on treatment will be seen in person monthly. *It is permissible and encouraged that patients who a treating physician feels may be at higher than average risk for toxicity from afatinib should be seen at one extra in-person visit, 1 week after starting study therapy (on cycle 1 day 8).*

Radiographic assessment of responses will be performed via CT scans of the chest/abdomen/pelvis every 8 weeks until disease progression is observed or until drug intolerance.

## **6.2 DETAILS OF STUDY PROCEDURES AT SELECTED VISITS**

### **6.2.1 Screening period**

Baseline evaluations are to be conducted within 21 days prior to start of protocol therapy. See the Flow Chart for details of required screening procedures.

## **6.3. REGISTRATION PROCEDURES**

### **6.3.1 General Guidelines**

All eligible patients will be registered centrally by the University of Chicago Clinical Research Associate assigned to the study. All sites should call the CRA to verify availability of a slot. Following registration, patients should begin protocol treatment within the window specified in 6.2.1. Issues that would cause treatment delays should be discussed with the Lead Principal Investigator. If a patient does not receive protocol therapy following registration, the patient's registration on the study may be canceled. The CRA should be notified of cancellations as soon as possible.

### **6.3.2 Registration Process**

#### **Pre-registration for Screening**

- All patients must be pre-registered with the UC Phase II coordinator to obtain a screening ID number. This ID number will be used for the screening mutation testing involved on this trial. Please email the UC Phase II coordinator at [[contact]](mailto:[contact]) to obtain this screening number.

#### **Treatment Registration**

Once the signed informed consent has been obtained, all pretreatment evaluations have been performed, and patient's eligibility has been confirmed by the University of Chicago a patient will be registered on study.

When a potential patient has been identified, notify the CRA via phone or email to ensure a reservation on the study. Reservations for potential subjects will only be held for subjects who have signed consent for that particular study.

To register a patient, the research nurse or data manager must complete the eligibility/registration form and contact the central study office at the University of Chicago ([contact]) or fax a copy of the completed eligibility checklist, signed Informed Consent, medical history documents, and results from the baseline evaluations ([contact]) or email (email preferred) to:

[[contact]](mailto:[contact])

When registering a subject, the following must occur:

- Confirm that the institution has current IRB approval of the correct version of protocol/consent and has an annual update on file.
- Submit all required materials (Eligibility Checklist, Source documentation, & signed consent form) to confirm eligibility and required pre-study procedures to the CRA a minimum of 48 hours prior to the subject's scheduled therapy start date.
- Source documentation includes copies of all original documents that support each inclusion/exclusion criteria. The eligibility checklist does not serve as source documentation but rather as a checklist that original source documentation exists for each criterion.
- Communicate with the above CRA to ensure all necessary supporting source documents are received and the potential subject is eligible to start treatment on schedule. If there are questions about eligibility, the CRA will discuss it with the PI. PI may clarify, but not overturn, eligibility criteria.
- Affiliate sites must confirm registration of subjects by obtaining a subject study ID number from the CRA via phone, fax or email.
- If a subject does not start on the scheduled day 1 treatment date, promptly inform the CRA as the delay in start may deem the subject ineligible and/or require further or repeat testing to ensure eligibility.
- The date the patient is randomized if randomization is involved or receives treatment for the first time will be considered the patient's "OnStudy Date." The patient's subject ID will be assigned and a confirmation of registration will be issued by the CRA on this date. Subjects that sign consent and do not go "OnStudy" will be recorded in the database with the date they signed consent and the reason for not going "OnStudy" (e.g., Ineligible, Screen Failure or Withdrawn Consent).

